#### 5.4 Measurable Residual Disease Assessment

MRD assessment by clonoSEQ® requires an initial marrow sample containing myeloma cells for identification of myeloma-specific sequences in IGH-VDJ, IDH-DJ, and/or IGK. During screening, a fresh bone marrow sample or archive, non-stained bone marrow aspirate slide ("ID sample") will be sent to Adaptive Biotechnologies to be assessed for the presence of myeloma-specific sequences.

For all samples with MRD assessment, MRD will be reported quantitatively as proportion of multiple myeloma-associated sequences. For treatment assignment and clinical trial outcome reporting, we will consider MRD-negative if the burden of MM-associated molecules is  $\leq 10^{-5}$ .

Subjects who achieve confirmed MRD(-) status with ≤10^-5 MM-associated molecules during maintenance will undergo FDG PET/CT scan. FDG PET/CT will be interpreted by the enrolling site and reported on data forms.

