Secondary Endpoints	
 
Best objective response on the trial (by IMWG criteria).
 
Progression-free survival.
 
Negative MRD (≤10^-5, by clonoSEQ®), including imaging plus MRD-negativity (≤10^-5 in bone marrow and no area of PET-CT FDG uptake greater than mediastinal blood pool or surrounding normal tissue).
 
Duration of response on maintenance.
 
Time to progression/relapse after CAR-T.
 
Overall survival for the entire study population.
 
Adverse events on the trial.
 
QoL parameters.
 
					
Exploratory Objectives	Exploratory: BCMA expression by flow cytometry and soluble     BCMA/BAFF/APRIL levels will be monitored at screening/baseline, and     after two, six, and 12 cycles.					
Exploratory Endpoints	Baseline and on-treatment sBCMA/BAFF/APRIL and BCMA expression on myeloma cells.					
Study Design	This is a multicenter phase II, open-label study evaluating the efficacy and safety of belantamab mafodotin maintenance in participants with RRMM who have received commercially available anti-BCMA CAR-T-cell therapy.  Subjects will be enrolled 60–120 days after CAR-T and receive belantamab mafodotin as maintenance therapy. Although screening can occur as early as day 60 post CAR-T therapy, study treatment cannot be started prior to day 90 post CAR-T therapy. Each maintenance cycle will have a duration of 56 days (+/- three days) and belantamab mafodotin will be administered at a dose of 1.9 mg/kg IV on day 1 of each cycle. The study will enroll up to 45 subjects with an interim analysis performed when 23 patients have been treated and followed to the 12th month after					

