- 16. NGS for MRD assessment (clonoSEQ®) will be performed on bone marrow aspirate sample. Bone marrow aspiration with MRD assay (first pull, in subjects found to be MRD-informative based on clone identification sample) and flow cytometry/cytotoxicity assays will be performed within seven days before cycle 3 day 1, and cycle 7 day 1 and within seven days before or after cycle 12 day 56. Samples are also to be obtained/sent for correlative studies (refer to Appendix 5).
- 17. Patient-reported outcomes (refer to Appendix) PRO assessments should be completed before any other study procedures are performed (except for blood draws).:
  - a. EORTC-QLQ-MY20 and EORTC QLQ-C30
    - i. Collect at cycle 1 day 1 (prior to treatment), cycle 3 day 1, cycle 7 day 1, cycle 9 day 1, and 70-day safety visit.
  - b. OCULAR SURFACE DISEASE INDEX (OSDI)
    - i. Collect at cycle 1 day 1 (prior to treatment), every cycle day 1, and 70-day safety visit.
- 18. For patients who discontinue treatment prior to progression, continue standard-of-care follow-up every three months until progression or start of another treatment (whichever comes first), then continue to long-term follow-up.
- 19. Long-term survival data collected/reported approximately every six months (+/- 30 days).
- 20. Urine dipstick for protein may be used to assess for presence of urine protein. Albumin/creatinine ratio needs to be done in any participant with urine dipstick result of ≥1+ at screening, or with positive protein if urine dipstick protein quantification is not available.

Short Title: MCW EMBRACE TRIAL 15 Version No.: 3
Version Date: 12/29/2022

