#### 2.4 **Secondary Endpoints**

- 1. Best objective response on the trial (by IMWG criteria).
- 2. Progression-free survival.
- 3. Negative MRD ( $\leq 10^{-5}$ , by clonoSEQ®), including imaging plus MRD-negativity ( $\leq 10^{-5}$  in bone marrow and no area of PET-CT FDG uptake greater than mediastinal blood pool or surrounding normal tissue.
- 4. Duration of response on maintenance.
- 5. Time to progression/relapse after CAR-T.
- 6. Overall survival for the entire study population.
- 7. Adverse events on the trial.
- 8. QoL parameters.

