#### **Secondary outcomes**

Time-to-event outcomes, such duration of response, time to progression/relapse, progression-free survival, and overall survival will be described using the Kaplan-Meier estimator. Left truncation at the start of study treatment will be used. Best objective response on the trial and negative MRD prevalence at specific timepoints will be summarized as counts with percentages. Quality of life scores will be summarized at each timepoint with descriptive statistics and analyzed using mixed effect models with a random subject intercept.

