#### APPENDIX 5. CORRELATIVE SAMPLE INSTRUCTIONS AND **REOUISITION FORM**

# **Methods for Preparation of Samples**

#### **1.0** Bone Marrow

A. ~10 ml of bone marrow aspirate from each patient should be collected in heparinized tube at each of the timepoints below, stored at room temperature, and shipped overnight at room temperature.

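### MRD-negativity has no minimum sample sensitivity, so a low-input marrow showing zero clonal molecules counts as negative at 10^-5 without having been tested to that depth

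*Combined protocol and SAP*

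**What the plan says.** Section 5.4 says that "MRD will be reported quantitatively as proportion of multiple myeloma-associated sequences", and for outcome reporting "we will consider MRD-negative if the burden of MM-associated molecules is" at most 10^-5. The secondary endpoint uses the same cut-off: "Negative MRD (≤10 -5 , by clonoSEQ®), including imaging plus MRD-negativity". For the combined version, the body text (Section 2.4) asks for the marrow result "in bone marrow and no area of PET-CT FDG uptake greater than mediastinal blood pool or surrounding normal tissue". PET-CT is the only element added.

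The conditions on the MRD sample are in Section 5.4 (an identification sample with a trackable sequence) and in footnote 16 of the study calendar: "first pull, in subjects found to be MRD-informative based on clone identification sample". These cover which aspirate is used and whether a clone can be followed. They do not set a number of cells or a depth.

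Under the secondary outcomes in Section 8.2.5, "negative MRD prevalence at specific timepoints will be summarized as counts with percentages". No section states a minimum input, a sensitivity that the sample must reach, a class for inadequate samples, or the denominator of the percentage.

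**The concern.** The rule looks only at the observed proportion. Zero clonal molecules gives a proportion of zero whatever the number of cells examined, so the rule cannot tell disease shown to be below 10^-5 from disease not looked for at 10^-5. A cut-off of 10^-5 is naturally read as a statement about the second, and a reader of the results will take it that way.

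MRD elimination is a named secondary objective in a single-arm trial of at most 45 patients, so there is no comparator to show up negatives that come from thin samples. One patient in 45 is 2.2 percentage points, and the number assessed at cycles 3, 7 and 12 may be smaller. Counts and percentages alone would not let a reader see which negatives rest on adequate samples.

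**Working it through.** **Plan's own figure.** There is none to reproduce. The documents give no cell input, sensitivity or power for MRD. The 10^-5 cut-off is a definition (Section 5.4).

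**Inputs**
- Cut-off T = 10^-5 (Section 5.4).
- N, the cells evaluated in one sample. This is not in the documents and is assumed to range from 20,000 to 300,000.
- f, the true burden, illustrated at 3 x 10^-5, three times the cut-off (assumption).
- Simplifications: one tracked molecule per myeloma cell, perfect recovery, Poisson sampling.

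**Formulas**
- Probability of zero molecules: P0 = exp(-N x f).
- 95% upper limit on the burden after zero molecules: -ln(0.05)/N, about 3/N.
- Cells needed for zero molecules to exclude 10^-5 with 95% confidence: -ln(0.05)/10^-5 = 299,573, about 300,000.

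**Results**

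| N | 95% upper limit after zero molecules | Multiple of cut-off | P0 at f = 3 x 10^-5 |
|---|---|---|---|
| 20,000 | 1.5 x 10^-4 | 15 | exp(-0.6) = 55% |
| 50,000 | 6 x 10^-5 | 6 | exp(-1.5) = 22% |
| 100,000 | 3 x 10^-5 | 3 | exp(-3) = 5% |
| 300,000 | 1 x 10^-5 | 1 | exp(-9) = about 0.01% |

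An exact binomial check at N = 20,000 and f = 5 x 10^-5 gives 0.368, the same as exp(-1).

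**The opposite error.** Below 100,000 cells a single molecule reads above 10^-5 (1/100,000 = 10^-5). A patient truly below the cut-off, at 5 x 10^-6, is then called positive with probability 1 - exp(-N x 5 x 10^-6):
- N = 50,000: 1 - exp(-0.25) = 22%.
- N = 20,000: 1 - exp(-0.1) = 9.5%.

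At 50,000 cells this equals the 22% chance of missing a true burden of 3 x 10^-5.

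**Effect of a floor.** With at least 300,000 cells, zero molecules at a true burden of 10^-5 has probability 5%, and at 2 x 10^-5 it is 0.2%.

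**The case against.** The strongest reply is that the size is assumed. Nothing in the documents suggests that 20,000-cell samples will occur, the assay is a named one sent to a named laboratory, and the first pull limits haemodilution. At about 300,000 cells the zero-molecule problem all but disappears. The endpoint is secondary and summarised without a test. The primary PFS comparison, the futility rule and the sample size do not use it. All of this stands and limits the weight of the point. It does not supply the missing condition, because neither a first pull nor a trackable clone sets a depth.

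A reader might infer more than the documents support in four ways.

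- **That the error flatters the drug.** It need not. Low input also produces false positives, as shown above. MRD is measured at screening too, where a poor sample can hide disease and remove a patient from those able to show elimination. Nothing indicates that on-treatment sampling will be worse than baseline.
- **That the correlative draw starves the MRD assay.** Appendix 5 says "10 ml of bone marrow aspirate from each patient should be collected in heparinized tube at each of the timepoints below", but that is the correlative tube, and footnote 16 gives the first pull to MRD. No section shows MRD input being reduced.
- **That the misclassification is larger at higher inputs.** Applying the at-or-below rule to any count gives 20% at 100,000 cells and 2% at 300,000 for a true burden of 3 x 10^-5. Those figures include samples with one or more molecules (up to three at 300,000). They are not the zero-molecule case, which gives 5% and about 0.01%. The 2% would remain after a floor of 300,000. Section 2.3 also prints the cut-off as strictly below 10^-5, under which one molecule in exactly 100,000 would not be negative.
- **That one negative read triggers PET-CT.** Section 5.4 refers to "Subjects who achieve confirmed MRD(-) status with" a burden at or below the cut-off. Confirmation is not defined, but the text does not say that one read is enough. In the combined endpoint PET-CT may catch some cases; the marrow-only endpoint has no such check.

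**Conclusion.** The point holds as a gap in the definition. Section 5.4 gives a complete rule, and under it a zero-molecule sample of any size is MRD-negative. If inputs fall to 50,000 cells or fewer, such a result is compatible with a true burden six or more times the cut-off, and a patient at three times the cut-off is missed 22% of the time or more. At 100,000 cells the miss rate is 5%, and at 300,000 it is negligible.

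These figures rest on Poisson sampling, one molecule per cell, full recovery and an assumed range of cell inputs. The frequency of low-input samples cannot be judged from the documents, so neither the number of patients misclassified nor the net direction of the bias can be stated. The consequence is confined to a descriptive secondary endpoint and its combined form with imaging. It is worth correcting because the correction is cheap and should be settled before any MRD results are read.

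**What to change.** In Sections 5.4 and 8.2.5:

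1. Score a sample MRD-negative only if the read-out is at or below 10^-5 and that sample reached a sensitivity of 10^-5 or better (about 3 x 10^5 cells evaluated).
2. Class a read-out at or below 10^-5 with lower sensitivity as not evaluable.
3. Report the MRD-negative rate at each timepoint with all MRD-informative patients assessed at that timepoint as the denominator. Not-evaluable samples count as not negative and are shown as a separate count.
4. Also report the rate among adequate-input samples only, applying the input floor to positives and negatives alike. Dropping low-input negatives while keeping low-input positives would itself bias this rate downward.
5. Record cells evaluated, or the sensitivity reached, on the MRD data form.

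The cost is a few lines of wording and one data field. It assumes that the laboratory reports cells evaluated or sensitivity for each sample. The documents do not say so, and this should be confirmed with the laboratory. The downside is that some samples become not evaluable and the reported negative rate may be lower. If every sample is adequate, the result does not change.

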#### 5.5 General Concomitant Medication and Supportive Care Guidelines

Concomitant treatments and/or procedures that are required to manage a subject's medical condition during the study will also be recorded in the eCRF.

#### 5.6 Prohibited Medications

The following medications are prohibited:

- Any concomitant anticancer therapy to treat the disease under study.
- Any investigational study drug, for any indication.
- Concomitant administration of strong P-glycoprotein (P-gp) inhibitors and strong inhibitors of OATP (see link below) with belantamab mafodotin should be avoided unless considered medically necessary.
  - Refer https://www.fda.gov/drugs/drug-interactions-labeling/drugdevelopment-and-drug-interactions-table-substrates-inhibitors-and-inducers
- Unless directed by an opthalmologist, contact lenses are not allowed for participants while they are receiving belantamab mafodotin treatment.
  - o Contact lens use may be restarted after discontinuation of belantamab mafodotin treatment, provided the eye care specialist confirms there are no other contraindications.
- Administration of live or live-attenuated vaccines are contraindicated 30 days prior to the first dose of study treatment. Use of live or live-attenuated vaccines is further contraindicated for at least 70 days following the last dose of belantamab mafodotin. Killed or inactivated vaccines may be administered; however, the response to such vaccines cannot be predicted.

#### **5.7 Monitoring Subject Compliance**

Study drug will be administered or dispensed only to eligible patients under the supervision of the investigator or identified sub-investigator(s). The appropriate study personnel will maintain records of study drug receipt and dispensing. Comprehensive instructions may be provided to the patient in order to ensure compliance with dosing procedures.

#### 5.8 Follow-up Period

For patients who discontinue treatment prior to progression, continue standard-of-care follow-up every three months until progression or start of another treatment (whichever comes first), then continue to long term follow-up.

All patients will be followed for survival and follow-up data every six months (± 30 days) until withdrawal of consent, loss to follow-up, death, or the end of the study, whichever occurs first.

Refer to section above regarding ocular examination and procedures during follow-up.

## 6 ADVERSE EVENTS: DEFINITIONS, COLLECTION, AND REPORTING REQUIREMENTS

#### 6.1 Definitions

#### **6.1.1 Adverse Event**

Any untoward medical occurrence in a patient or clinical investigation subject administered a pharmaceutical product and which does not necessarily have to have a causal relationship with this treatment. (International Conference on Harmonisation [ICH], E2A, E6).

This study will utilize the NCI Common Terminology Criteria for Adverse Events (CTCAE) version 5.0, located on the CTEP web site:

https://ctep.cancer.gov/protocolDevelopment/electronic applications/ctc.htm

AEs may be spontaneously reported by the patient and/or in response to an open question from study personnel or revealed by observation, physical examination or other diagnostic procedures.

#### **6.1.2 Serious Adverse Event (SAE)**

Serious adverse event (SAE) means any untoward medical occurrence that results in any of the following outcomes:

- **Death.** Results in death.
- Life-threatening. Is life-threatening (refers to an AE in which the patient was at risk of death at the time of the event. It does not refer to an event which hypothetically might have caused death if it were more severe).
- Hospitalization. Requires inpatient hospitalization or prolongation of an existing hospitalization (see clarification in the paragraph below on planned hospitalizations).
- Disability/incapacity. Results in persistent or significant disability or incapacity. (Disability is defined as a substantial disruption of a person's ability to conduct normal life functions).
- A congenital anomaly/birth defect.
- **Medically important event.** This refers to an AE that may not result in death, be immediately lifethreatening, or require hospitalization, but may be considered serious when, based on appropriate medical judgment, may jeopardize the patient, require medical or surgical intervention to prevent one of the outcomes listed above, or involves suspected transmission via a medicinal product of an infectious agent. Examples of such medical events include new invasive or malignant cancers

(excluding the disease[s] under study in oncology protocols, e.g., secondary malignancies), allergic bronchospasm requiring intensive treatment in an emergency room or at home, blood dyscrasias or convulsions that do not result in inpatient hospitalization, or the development of drug dependency or drug abuse; any organism, virus, or infectious particle (e.g., prion protein transmitting transmissible spongiform encephalopathy), pathogenic or nonpathogenic, is considered an infectious agent. Secondary malignancies should always be considered as serious adverse events.

- **Liver toxicity** (as follows):
  - ALT absolute ALT  $\geq$  5xULN.
  - ALT  $\ge 3$ xULN persists for  $\ge$  four weeks.
  - o ALT  $\geq$  3xULN and total bilirubin  $\geq$  2xULN (>35% direct bilirubin).
    - Serum bilirubin fractionation should be performed if testing is available; if unavailable, measure urinary bilirubin via dipstick. If fractionation is unavailable and ALT  $\geq$  3 x ULN and total bilirubin  $\geq$  2 x ULN, then the event is to be reported.
  - ALT  $\geq$  3xULN and INR>1.5.
    - INR testing not required per protocol and the threshold value does not apply to participants receiving anticoagulants. If INR measurement is obtained, the value is to be recorded when reporting.
  - o ALT  $\geq$  3xULN and cannot be monitored weekly for four weeks.
  - $\circ$  ALT  $\geq$  3xULN associated with symptoms (new or worsening) believed to be related to liver injury or hypersensitivity.

#### 6.1.3 Attribution of an Adverse Event

For all collected AEs, the site investigator who examines and evaluates the subject will determine the adverse event's causality to all of the study drugs, based on temporal relationship and his/her clinical judgment. The degree of certainty about causality will be graded using the categories below:

- **Definitely Related:** There is clear evidence to suggest a causal relationship, and other possible contributing factors can be ruled out.
- Probably Related: There is evidence to suggest a causal relationship, and the influence of other factors is unlikely.
- **Possibly Related:** There is some evidence to suggest a causal relationship (e.g., the event occurred within a reasonable time after administration of the trial medication). However, the influence of other factors may have contributed to the event (e.g., the subject's clinical condition, other concomitant events).
- Unlikely: A clinical event, including an abnormal laboratory test result, whose temporal relationship to study agent administration makes a causal relationship improbable (e.g., the event did not occur within a reasonable time after administration of the trial medication) and in which other drugs or chemicals or underlying disease provides plausible explanations (e.g., the subject's clinical condition, other concomitant treatments).
- Unrelated: The AE is completely independent of study agent administration, and/or evidence exists that the event is definitely related to another etiology.

While sites report to the MCW sponsor-investigator based on the above categories, the MCW sponsorinvestigator reports to the funder (GSK) based on the categories "related" or "not related" attribution:

Related: There is a reasonable possibility of a causal relationship between the medicinal product and AE, i.e., there are facts, evidence, and/or arguments to suggest a causal relationship, rather than a relationship cannot be ruled out. Alternative causes, such as underlying disease(s), concomitant therapy, and other risk factors, as well as the temporal relationship of the event to study treatment

Short Title: MCW EMBRACE TRIAL Version No.: 3 53 Version Date: 12/29/2022

- administration will be considered and investigated.
- Not Related: A causal relationship between the medicinal product and the AE cannot be established, based on consideration of factors described above.

#### 6.1.4 Expectedness of an Adverse Event

Each site investigator will decide whether an adverse event (AE) is expected or unexpected, but the sponsor is ultimately responsible for determination of expectedness and may therefore override the site investigator's determination of expectedness.

#### 6.2 Collection and Reporting Requirements for Adverse Events and Serious Adverse Events

#### **6.2.1 Collection of Adverse Events**

All adverse events (including SAEs) must be recorded in OnCore® data forms. All AEs required to be collected must be graded according to the CTCAE v5. Investigator's or treating physician's assessment of AE attributions must also be documented.

SAEs and AEs will be collected and reported after first treatment dose, through 70 days post last dose of belantamab mafodotin. All conditions prior to treatment will be considered baseline, medical history unless changing in grade after treatment. AEs will be tracked and followed until resolution, subject withdraws consent, or is lost to follow-up (including subjects who discontinue early).

#### 6.2.2 Reporting of Adverse Events, Serious Adverse Events, and AEs of Special Interest (AESI)

	All SAEs (including liver toxicity defined in Section 6.1.2)	
Events requiring expedited reporting (i.e., requiring immediate action)	Non-hematological grade 4 AEs not meeting SAE definition.	
	Unanticipated problems involving risks to participants or others (UPIRSO).	
	Pregnancy.	
	Deviations that are "significant" (affect subject safety, such as medication errors) or planned.	
	Action letter from sponsor.	
	Product complaint.	
	Subject trial withdrawal.	
Events requiring routine reporting (i.e., entered into OnCore® in a timely manner)	All grade 1–4 AEs (unless in an above category), including all lab abnormalities (regardless of clinical significance) and AEs of special interest (AESI).  Non-significant deviations.	

